9.2 Analysis of Exploratory Objectives

- 9.2.1 For Objective 2.2.1, frequencies will be used to summarize the number and type of referrals selected by intervention caregivers. Referral adherence will be defined as completion of referral (i.e. services utilized) within the caregiver's duration of study participation. Frequencies will also be used to summarize the number of intervention caregivers who adhered to referrals selected, among those who selected an automatic referral. This percentage will be calculated for caregiver-reported adherence as well as service administrator-reported adherence and concordance among caregiver- and - service administrator reported adherence will be calculated using McNemar's test. Number of barriers to supportive care use will be summarized using descriptive statistics (mean and standard deviation) and compared between intervention and control caregivers using an independent samples t-test.
- 9.2.2 For Objective 2.2.2, we will calculate descriptive statistics by arm and the difference between arms for the variables of interest at T0, T1 and T2, and change in variables from T0-T2 to provide estimates of variance for a larger study. We will examine differences by arm but are not powered for hypothesis testing at a 0.05 alpha-level between the two arms.
- 9.2.3 For Objective 2.2.3, we will examine change in supportive care resource use with change in the caregiver outcome variables (perceived care quality, burden, and distress, quality of life, caregiving self-efficacy, and self-care) using a regression approach to examine whether changes in supportive care resource use are associated with change in the outcomes.

CONNECTing Caregivers to Supportive Services (CONNECT):
A Technology-Based Intervention to Connect Cancer Caregivers with Supportive Care
Resources

Wake Forest Baptist Comprehensive Cancer Center
WFBCCC # 99519

- 9.2.4 For Objective 2.2.4, we will model changes in patient physical well-being and the patient healthcare utilization score at T1 and T2 as a function of change in caregiver psychosocial functioning from baseline using mixed effects models for the outcomes of interest with the baseline value of the outcome, change in caregiver burden and distress, arm, and time as the predictors.
- 9.2.5 A mixed model with a random family effect will also be used to characterize dyadic relationships between patients and caregivers for distress and perceived care quality for Objective 2.2.5.

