3.2 Exploratory Objective(s)

- 3.2.1 To assess adherence to referrals for supportive care resources (caregiver- and administrator-reported) among intervention caregivers (n = 20) and barriers to supportive care use among intervention and comparison (n=40) caregivers.
- 3.2.2 To obtain preliminary data on HNC caregiver outcomes (supportive care service use, perceived care quality, burden, and distress, quality of life, caregiving self-efficacy, and self-care) and HNC patient outcomes (physical well-being, unplanned healthcare utilization, perceived care quality, distress, and symptoms)..

CONNECTing Caregivers to Supportive Services (CONNECT):
A Technology-Based Intervention to Connect Cancer Caregivers with Supportive Care
Resources

Wake Forest Baptist Comprehensive Cancer Center
WFBCCC # 99519

- 3.2.3 To examine changes in the caregiver outcome variables (perceived care quality, burden, distress, quality of life, caregiving self-efficacy, and self-care) with changes in in supportive care resource use.
- 3.2.4 To examine if patient physical well-being and patient healthcare utilization are associated with change in caregiver burden and distress in intervention arm caregivers.
- 3.2.5 To characterize the correlation between caregivers and patients with regard to distress and perceived care quality.

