6.2.1.1.10 Caregiver Adherence to Referral

Survey developed for purpose of this study to examine referral details. This includes date referral received by agency, time point of referral (T0/2 week follow up), if participant utilized services, and date those services were initially accessed. In addition, intervention caregivers will also self-report service use by completing an auto-generated REDCap survey to query about utilization of the specific resources that each caregiver expressed interest in accessing

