CONNECT is a web-based intervention designed to empower caregivers with needs who are caring for cancer patients to seek supportive care services by providing education about the benefits of supportive care resources, systematically identifying their unmet needs, and connecting them with tailored supportive care resources, based on each caregivers' specific needs. Caregivers will be recruited in conjunction with the patient's routine oncology appointment. Following recruitment, dyads will complete the T0 assessment and caregivers will be randomized to CONNECT or the comparison group. CONNECT includes a multi-component e-tool accessible by a study website. CONNECT includes a multi-component web-based tool with the following: (1) a brief educational video (Appendix N) that seeks to empower and educate caregivers about the importance of self-care and benefits of supportive care resource use; (2) an assessment of multidimensional supportive care needs (e.g., psychological, behavioral, social, financial, educational, spiritual) (Appendix O); (3) a tailored resource list that includes local and national resources corresponding to caregivers' needs (Appendix P) (Table1); and (4) an optional automated referral to a caregiver navigator to facilitate connection to resources (for a limited number of resource options). Caregivers and patients will each receive a \$20 gift card for each assessment (T0, T1, and T2).

Table 1. Examples of Supportive Identified Needs and Matched Resources

Identified Need	→	Matched Resource
Psychological support		WFBCCC Cancer Patient Support Program
Tobacco cessation		WFBCCC Tobacco Cessation Clinic
Financial counseling		Winston-Salem Cancer Support Services
Cancer Education		American Cancer Society handbook for cancer caregivers

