Adherence to referrals for supportive care services will also be tracked by each participating resource in a study spreadsheet (Appendix U). We will collect name, date referral was received, if service was accessed, and date service accessed. This spreadsheet will be collected by email quarterly throughout the study period.

Refusal Data Collection

If participants refuse to participate in the study, we will ask them to fill out a brief questionnaire with the following information: age, race, ethnicity, gender, marital status, education level, employment status, why they chose not to participate, and rating their distress in the past week (Appendices V and W)

**CONNECTing Caregivers to Supportive Services (CONNECT):
A Technology-Based Intervention to Connect Cancer Caregivers with Supportive Care Resources**
Wake Forest Baptist Comprehensive Cancer Center
WFBCCC # 99519

Table 2. Assessment Plan

Assessment	Time	Description
Caregiver sociodemographics & caregiving characteristics *	T0, T1, T2	Age, gender, race/ethnicity, education, employment status and impact, income and financial impact, insurance status, marital status, living with patient (yes/no), relationship to patient, respite assistance (yes/no)
Patient sociodemographics *	T0, T1, T2	Age, gender, race/ethnicity, education, employment status, and insurance status
Patient clinical information	T0	Time since diagnosis, AJCC Stage, and treatment history for current cancer diagnosis
Accrual	T0, T1, T2	Number of caregivers who agreed to participate divided by the number of months of recruitment
Participation	T0, T1, T2	Proportion of eligible participants who agreed to participate
Retention	T0, T1, T2	Number of participants who completed the T2 assessment divided by the number who agreed to participate
Caregiver acceptability	T1	Survey developed for study to assess how much caregivers liked different aspects of CONNECT; and a ~30min (approximately) qualitative interview to further explore acceptability.
Caregiver Measures		
Supportive Care Service Utilization	T0, T1, T2	Survey developed for the purpose of this study to query participants about utilization of supportive care services assessed as part of the CONNECT Preferences Survey. Participants will also self-report service use by selecting (yes/no) from a list of resource options consistent with the e-tool resource list.

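### McNemar's test is named as the way to calculate concordance between caregiver and administrator reports of referral adherence, but it does not measure agreement

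*Combined protocol and SAP*

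**What the plan says.** Section 9.2.1 defines the outcome as yes or no: "Referral adherence will be defined as completion of referral (i.e. services utilized) within the caregiver's duration of study participation". The analysis set is a subset of the intervention arm, because the plan counts "the number of intervention caregivers who adhered to referrals selected, among those who selected an automatic referral". Two summaries of the paired reports follow. The first is a rate per source: "This percentage will be calculated for caregiver-reported adherence as well as service administrator-reported adherence". The second is the comparison at issue: "concordance among caregiver- and - service administrator reported adherence will be calculated using McNemar's test".

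Both reports are to be collected. On the caregiver side, section 6.2.1.1.10 says "intervention caregivers will also self-report service use by completing an auto-generated REDCap survey to query about utilization of the specific resources". On the administrator side, section 7.3.3 says of each resource's tracking spreadsheet: "We will collect name, date referral was received, if service was accessed, and date service accessed".

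The documents name no percent agreement, kappa or other agreement coefficient for this comparison, and no cross-tabulation of the two reports. They do not say which version of McNemar's test applies, or how a caregiver who completed only some of several referrals enters the 2x2 table.

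**The concern.** Concordance is a statement about pairs: does the administrator's record for a caregiver match what that caregiver reports? McNemar's test discards the pairs that agree. It uses only the two discordant counts and tests whether disagreements fall equally in both directions, which is the same as testing whether the two sources have equal rates of yes. It can detect systematic over- or under-reporting by one source, but it cannot show how often they agree.

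The two adherence percentages do not fill the gap. They are the margins of the 2x2 table, and agreement cannot in general be recovered from the margins.

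There are two consequences. The quantity section 9.2.1 sets out to report would be absent from its stated outputs. And a non-significant p-value, which is likely with so few pairs, could be taken as evidence that self-report and administrator records agree. The pilot is meant to inform a larger trial (sections 2.0 and 9.0), and how well the two sources match bears on which of them that trial could rely on for adherence.

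**Working it through.** The documents give no figure for this analysis, so there is nothing to reproduce. They also give no expected referral or agreement rate, so the tables below are illustrations, not predictions.

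**Inputs.** The maximum number of pairs is 20, one per intervention caregiver (section 3.2.1). The referral is optional and covers only some resources (section 7.3.3), so the actual number may be smaller; 10 is used as an assumed lower case.

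**Notation.** a = both say yes, b = caregiver only, c = administrator only, d = neither; n = a+b+c+d.

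**Formulas.**
- Percent agreement: po = (a+d)/n.
- Kappa = (po − pe)/(1 − pe), where pe = [(a+b)(a+c) + (c+d)(b+d)]/n².
- Exact McNemar p = min{1, 2·P(Bin(b+c, 0.5) ≤ min(b,c))}.
- Uncorrected chi-square = (b−c)²/(b+c); continuity-corrected = (|b−c|−1)²/(b+c); each on 1 degree of freedom.

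**Results for n = 20.**

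| (a, b, c, d) | Adherent: caregiver / administrator | Agreement | Kappa | Exact p | Uncorrected p | Corrected p |
|---|---|---|---|---|---|---|
| (0, 10, 10, 0) | 50% / 50% | 0% | −1 | 1 | 1 | 0.82 |
| (5, 5, 5, 5) | 50% / 50% | 50% | 0 | 1 | 1 | 0.75 |
| (9, 1, 1, 9) | 50% / 50% | 90% | 0.80 | 1 | 1 | 0.48 |
| (4, 11, 5, 0) | 75% / 45% | 20% | −0.52 | 0.21 | 0.134 | 0.211 |
| (9, 6, 0, 5) | 75% / 45% | 70% | 0.43 | 0.031 | 0.014 | 0.041 |

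**First three rows.** The planned percentages and the exact p-value are identical throughout, while agreement runs from 0% to 90%. Enumerating every table of size 20, and of size 10, shows that an exact p of 1 is compatible with any agreement from 0% to 100%.

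**Last two rows.** For both, pe = 0.75 × 0.45 + 0.25 × 0.55 = 0.475.
- (4, 11, 5, 0): kappa = (0.20 − 0.475)/0.525 = −0.52; exact p = 2·P(Bin(16, 0.5) ≤ 5) = 0.21.
- (9, 6, 0, 5): kappa = (0.70 − 0.475)/0.525 = 0.43; exact p = 2 × 0.5⁶ = 0.031.

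The percentages are the same, agreement is very different, and under all three versions of the test the worse agreement has the larger p-value.

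**Power for the question the test does address.** Suppose all disagreement runs one way. Five such pairs give exact p = 0.0625 and six give 0.031, so at least six are needed for p < 0.05. If each caregiver has a 30% chance of being discordant in that direction, P(Bin(n, 0.3) ≥ 6) is 0.58 at n = 20 and 0.05 at n = 10. The uncorrected version needs four pairs, giving 0.89 and 0.35. A non-significant result would therefore often occur despite a real one-way difference.

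**The case against.** The strongest reply is that the method may be right and the word wrong. The sentence first plans one percentage per source and then names the standard test for two paired percentages. If the aim was to compare reporting rates, only the word concordance needs changing. Objective 3.2.1 asks for adherence by each source and does not itself ask for agreement. The text cannot settle what was intended, but the quantity it names is concordance, and following it does not deliver that. Under either reading the sentence has to change.

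It can also be said that the plan never equates a non-significant p-value with concordance, that building the test requires the 2x2 table anyway, and that the zero-agreement tables are implausible for two sources reporting on the same event. All of this is fair. The misreading is a risk, not something the plan commits; the plan does not, however, promise to report the table. The extreme tables prove a property of the test and do not forecast the trial, but the table with 50% agreement and kappa 0 makes the same point without an extreme assumption.

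A practical objection also stands in part. The schedule in section 7.2 places caregiver-reported referral adherence at T2 only, so caregivers lost before T2 cannot form a pair. At the 70% retention considered in section 9.3, about 0.70 × 20 = 14 caregivers would have T2 data, before restricting to those who chose a referral. The caregiver survey covers resources of interest while administrators record referrals received, so the two must be matched on referred resources. These points shape the fix; they do not remove the need for it.

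**Conclusion.** The concern holds. Section 9.2.1 assigns to McNemar's test a task it cannot do, and the adherence percentages beside it do not make up the difference. This follows from the definition of the test and does not depend on the illustrative tables, which only show how far apart the p-value and agreement can be.

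The consequence is limited. The analysis is exploratory, has at most 20 pairs if each caregiver counts once, and bears on no primary outcome or feasibility conclusion. The correction should be made because the mismatch is definite and the remedy nearly free. The missing rule for caregivers with several referrals is a related gap that affects the adherence percentages as well as the 2x2 table.

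**What to change.** Replace the concordance clause in section 9.2.1 with text such as:

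> Concordance will be reported from the 2x2 table of caregiver- by administrator-reported adherence, with one entry per caregiver who selected an automatic referral and has both reports, counting only referred resources. Percent agreement will be given with an exact 95% confidence interval, and Cohen's kappa with a 95% confidence interval as a supplementary measure where estimable. The exact McNemar test will be reported only as a check for directional over- or under-reporting by one source.

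Add a sentence saying how a caregiver with several referrals is classified, using the same rule for both sources (for example, adherent if at least one referred service was used), and report how many caregivers lack one of the two reports. If only a comparison of reporting rates was ever intended, the alternative is to keep the test and drop the word concordance.

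The cost is a few sentences of analysis text. Both reports are already planned under sections 6.2.1.1.10 and 7.3.3, and no change in sample size or visits is needed. The drawback is imprecision. In the (9, 6, 0, 5) table, 14/20 agreement has an exact 95% interval of 46% to 88%, and kappa of 0.43 (asymptotic standard error 0.160) has an interval of 0.11 to 0.74. Kappa is undefined if both sources give the same constant answer. For these reasons percent agreement should lead.

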4.0 Participant Selection

4.1 Inclusion Criteria

- 4.1.1 Eligible caregivers include those who are:
 - 4.1.1.1 Caregivers must be providing some capacity of informal (unpaid) care for a patient meeting patient eligibility criteria. If a patient unexpectedly becomes deceased during the study period, caregivers will be allowed to continue participation in the assigned study arm and complete study assessments if they wish to.
 - 4.1.1.2 Greater than or equal to 18 years of age.
 - 4.1.1.3 Ability to access study materials by internet or complete study activities in person as institutional and government policies allow.
- 4.1.2 Eligible patients include those who:
 - 4.1.2.1 Have new or recurrent AJCC stage I-IV HNC.
 - 4.1.2.2 Are receiving cancer treatment or awaiting planned treatment initiation, excluding those receiving neoadjuvant surgery or surgery only
 - 4.1.2.3 Patients must be ambulatory and up more than 50% of waking hours, as measured by an ECOG Performance Status rating of level 0, 1, or 2.
 - 4.1.2.4 Greater than or equal to 18 years of age.
 - 4.1.2.5 Ability to access study materials by internet or complete study activities in person as institutional and government policies allow.
 - 4.1.2.6 Patients must be receiving some capacity of informal care from a caregiver meeting the above criteria. If the caregiver unexpectedly becomes deceased during the study period, the patient will be un-enrolled from this study as we are evaluating a caregiver-only delivered intervention.

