Comparison Arm. Caregivers not randomized to the intervention group will receive minimally enhanced usual care. This includes a generic (not tailored) printed list of hospital, community, and national supportive care resources (Appendix R). They will not receive the video, complete the web-based tool Preference survey, or have an option for an automated referral. The generic resource list will be printed for participants and emailed to them, if participants have an email address.

Data Collection Procedures. Data collection and instruments are reported in Table 2. At T0, patient and caregiver sociodemographics and caregiving characteristics will be collected and patient clinical information will be abstracted from the electronic health record (EHR) (Appendix S). Feasibility data will be collected throughout the study period (T0-T2). Caregivers and patients will complete self-report quantitative assessments at T0-T2 through REDCap. We will email or text a link to complete the REDCap surveys at the appropriate times. To minimize missing data, we will call any participant who fails to complete a survey within 48 hours of the link being sent. In the case that a patient dies, caregivers may choose whether or not continue in the study and complete follow up questionnaires.

Data Management. All screened and approached participants will be recorded in an Excel document Appendix M. The responses of anonymous refusal surveys (Appendices V and W) will be recorded in a separate REDCAP Refusal project. All completed surveys for consented patients and caregivers will be recorded in an third REDCap project.

CONNECTing Caregivers to Supportive Services (CONNECT):
A Technology-Based Intervention to Connect Cancer Caregivers with Supportive Care
Resources

Wake Forest Baptist Comprehensive Cancer Center
WFBCCC # 99519

Qualitative Data Collection: At 2-weeks post-intervention - T1, caregiver qualitative interviews will be completed in person (or by telephone, if participant prefers) to assess acceptability of the intervention (est. 30min) using semi-structured guides with open-ended questions (Appendix T). During interviews, CONNECT elements will be reviewed and open-ended questions will be used to elicit feedback on functionality, strengths, and weaknesses of the web-based tool. All interviews will be audio-recorded and transcribed verbatim.

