9.3 Power and Sample Size

The sample size is based on feasibility, and we draw on our current patient-caregiver head and neck cancer protocol (PI: [name]; IRB00038084) at the WFBCCC, prior recruitment with HNC caregivers,^{13,51,52} and clinic estimates. Our primary feasibility measures are participation, accrual, and retention rates. Assuming a negative binomial distribution and true rate of 50%, the probability that we would approach ≥ 96 dyads to recruit 40 is <0.05 . If we approach ≥ 96 dyads to enroll 40, it is unlikely the true probability is 50% or greater, and we will conclude the study may not be feasible. We anticipate accruing 40 dyads within 9 months (4-5/month). A sample size of 40 achieves 92% power to detect a difference between a mean accrual rate of 4 participants/month and an alternative mean of 3 or fewer participants/month with a significance level of 0.025 using a two-sided one-sample Poisson test. Out of the 40 participants, if the true rate of retention is 70%, we expect 23 or more will be retained (i.e., probability of $n \leq 22$ successes is <0.05); we have 85% power to test that the hypothesis that the rate is 70% compared to 50%.

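### Section 9.2.2 names no baseline-adjusted arm difference for its 12 continuous scales, although all are measured at T0; the gain in precision from adding one is unknown and probably modest at T2

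*Combined protocol and SAP*

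**What the plan says.** Section 9.2.2 serves objective 3.2.2 (which it cites as 2.2.2). That objective begins "To obtain preliminary data on HNC caregiver outcomes (supportive care service use, perceived care quality, burden, and distress" and goes on to further caregiver and patient outcomes. For these, "we will calculate descriptive statistics by arm and the difference between arms for the variables of interest at T0, T1 and T2". The same sentence adds "change in variables from T0-T2 to provide estimates of variance for a larger study". The section then says "We will examine differences by arm but are not powered for hypothesis testing at a 0.05 alpha-level between the two arms". It names no covariate.

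Baseline values will be available. Under Data Collection Procedures in section 7.3.3, "Caregivers and patients will complete self-report quantitative assessments at T0-T2 through REDCap". The schedule in section 7.2 and Table 2 mark T0 for all 14 measures that objective 3.2.2 draws on. Twelve are scale scores:

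- Caregiver (7): FAMCARE, Caregiver Reaction Assessment, PROMIS anxiety, PROMIS depression, CqoL-Canc, self-efficacy, Caregiver Risk Scale.
- Patient (5): SF-12, FAMCARE, PROMIS anxiety, PROMIS depression, MDASI-HNC.

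The other two are caregiver service use and patient unplanned visits.

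Only section 9.2.4 uses a baseline covariate. It fits mixed models "with the baseline value of the outcome, change in caregiver burden and distress, arm, and time as the predictors", for patient physical well-being and the utilization score. Sections 9.2.3 and 9.2.5 name none.

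**The concern.** With about 20 dyads per arm, precision is scarce. If a scale at T1 or T2 is correlated with its own value at T0, an arm difference adjusted for T0 has a smaller standard error than the raw follow-up difference, once the correlation is large enough to repay the cost of estimating a slope. It also has a smaller standard error than the difference in change over most of the plausible range. Section 9.2.2 lists those two estimators and not the adjusted one.

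Section 9.2.4 does not fill the gap. It covers one of the 12 scales (SF-12 physical) plus the visit count. Its model also conditions on caregiver change after randomization, so its arm coefficient is not the arm difference that 9.2.2 reports.

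At stake is the width of exploratory intervals and the planning information passed to a larger study. The primary feasibility and acceptability results are not involved.

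**Working it through.** **Inputs.** Twenty caregivers per arm (sections 7.1 and 7.3.2). Section 9.3 considers 70% retention ("if the true rate of retention is 70%, we expect 23 or more will be retained"). The expected number is 0.70 × 40 = 28, or 14 per arm if losses are even. The documents give no SD, effect size or correlation for these outcomes, and no precision figure to reproduce. So r is an assumption, examined from 0 to 0.9, with equal SDs at each visit unless stated.

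**Formulas.** Let n be the number per arm, with the baseline SD set to 1 and the follow-up SD to k. Results are in follow-up SD units.

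- Raw: SE = √(2/n)
- Change: SE = √[(2/n)(1 + k² − 2rk)] / k
- ANCOVA: SE = √[(2/n)(1 − r²)(1 + 1/(2n − 4))]; the last factor is the cost of estimating the slope

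**Example, n = 20, r = 0.5, k = 1.** Raw is √0.1 = 0.316. Change is √(0.1 × 1) = 0.316. ANCOVA is √(0.1 × 0.75 × 37/36) = 0.278, and 0.278/0.316 is a 12.2% reduction. The 95% CI half-widths are 0.640, 0.640 and 0.563 SD (t with 38, 38 and 37 df).

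**20 per arm, equal SDs**

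| r | Raw | Change | ANCOVA | ANCOVA against better listed estimator at T2 | ANCOVA against raw (T1) |
|---|---|---|---|---|---|
| 0 | 0.316 | 0.447 | 0.321 | +1.4% (raw) | +1.4% |
| 0.2 | 0.316 | 0.400 | 0.314 | −0.7% (raw) | −0.7% |
| 0.3 | 0.316 | 0.374 | 0.306 | −3.3% (raw) | −3.3% |
| 0.5 | 0.316 | 0.316 | 0.278 | −12.2% (tie) | −12.2% |
| 0.7 | 0.316 | 0.245 | 0.229 | −6.5% (change) | −27.6% |

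At r = 0.9, change is √(0.1 × 0.2) = 0.141 and ANCOVA is √(0.1 × 0.19 × 37/36) = 0.140, about 1% smaller.

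**14 per arm.** Raw / change / ANCOVA are 0.378 / 0.447 / 0.368 at r = 0.3, 0.378 / 0.378 / 0.334 at 0.5, and 0.378 / 0.293 / 0.275 at 0.7. At r = 0 the ANCOVA SE is √(25/24) = 1.021 times raw, or 2.1% larger.

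**Break-even.** ANCOVA equals raw when (1 − r²)(2n − 3)/(2n − 4) = 1, so r = 1/√(2n − 3). That is 1/√37 = 0.164 at 20 per arm and 1/√25 = 0.200 at 14 per arm. Judged by CI width, with one degree of freedom lost, these become 0.170 and 0.209. With equal SDs, ANCOVA also beats change up to r of about 0.95 (40 completers) or 0.92 (28).

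**Unequal SDs.** Patients "Are receiving cancer treatment or awaiting planned treatment initiation", so spread may differ between visits. Raw and ANCOVA do not move in follow-up SD units, but change does. At r = 0.5 and 20 per arm, the change SE is 0.362 for k = 0.8 and 0.290 for k = 1.25. At r = 0.7 and k = 1.25 it is √[0.1 × (1 + 1.5625 − 1.75)]/1.25 = 0.228, against 0.229 for ANCOVA, so the gain over change is about nil.

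**Simulation check.** With 200,000 trials per setting, the ANCOVA to raw variance ratio at r = 0.5 was 0.770 (40 completers) and 0.782 (28). The formula gives 0.771 and 0.781.

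**The case against.** The best case for leaving 9.2.2 alone has four parts.

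- **Baseline is already used.** The T0-T2 change draws on T0, and the natural reading is that arm differences cover it. This stands. A reader might quote the 27.6% reduction as the general gain, but that figure is against the raw difference at r = 0.7, and so applies only at T1. At T2 the fair comparator is the better of raw and change, and with equal SDs the gain peaks at about 12% near r = 0.5.
- **The planning quantities can be recovered.** With SDs on the same completers, r = (s₀² + s₂² − s_change²)/(2s₀s₂). The residual SD is then about s₂√(1 − r²). With pooled within-arm SDs, the adjusted T2 difference is about D₂ − (r s₂/s₀)D₀, where D₀ and D₂ are the arm differences at T0 and T2. This stands for T2, provided all those SDs are reported on the same people. It fails for T1, because no T0-T1 change is listed.
- **Nothing depends on it.** The section is exploratory and disclaims power. This also stands, and it is why the point is an optional improvement.
- **The benefit rests on an assumed r.** That is true, but the trade is uneven. The worst case is an SE 1.4% to 2.1% larger than raw, while r = 0.5 gives about 12% at 20 per arm. The break-even of about 0.2 is not a reason against adjusting.

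A reader might also infer that the raw differences are biased or that the later trial will be mis-sized. Neither follows. Under randomization the raw difference is unbiased, and the documents contain no sizing calculation for the larger study that this omission could distort.

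**Conclusion.** The omission is real and confined to the 12 continuous scales in 9.2.2. Adjustment would give a tighter estimate than either listed estimator if r lies above about 0.16 to 0.20 and below about 0.92 to 0.95, assuming equal SDs, approximately normal scores and even losses between arms. The size of the gain in this trial cannot be stated from the documents. Under those assumptions it ranges at T2 from a trivial loss to about 12% of the SE, and at T1 it could be larger. If the SD rises by a quarter between visits, the T2 advantage over change can vanish. The yes/no service-use items and the count of unplanned visits are outside the calculation. This is a low-priority improvement to an exploratory analysis and leaves the primary objectives untouched.

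**What to change.** Keep every planned descriptive and add to section 9.2.2:

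> For continuous outcomes measured at T0, the main estimate of the arm difference at T1 and T2 will be adjusted for the outcome's baseline value (ANCOVA at each visit, or one repeated-measures model with arm, time, arm-by-time and baseline), with a 95% CI, for estimation and not hypothesis testing; raw and change differences are descriptive. The residual SD and the T0-T1 and T0-T2 correlations will be reported.

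Naming one main estimate matters: without it, three versions of each difference would sit side by side and invite selective emphasis. Leave unplanned visits and yes/no service use descriptive.

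The cost is 12 × 2 = 24 ANCOVA models, or 12 repeated-measures models, and more if subscales are reported. The precision figures above are for ANCOVA; none was calculated for the repeated-measures option. No new data, visits or questionnaires are needed.
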